Study Design. Participation starts with a simple information sheet, online eligibility survey, orientation webinar, e-consent, and then another survey to collect baseline assessment data. Eligible participants will then complete an on-boarding process, which includes MyFitnessPal and scale set up. Participants will then be randomized (stratified by gender) and complete an 8-week intervention, and then two assessments at 9-weeks (weigh-in, survey) and 12-weeks (weigh-in).

Recruitment. We will post online recruitment ads that will contain a link to a simple information sheet and an online survey containing the screening questions. Ads that are done with Build Clinical will lead the participants to a landing page that will give them some more information about the study and then will have the link to bring them to the simple information sheet and survey. See the recruitment section (starting on page 6) for full recruitment details.

Screening. Participants will complete screening procedures online since they may be located anywhere in the country. The screening survey will first have a description of the study and the data we will collect from them at that point (the simple information sheet). At the bottom of the information sheet, they can mark whether they are interested in participating or not

interested. If they mark that they are interested, it will bring them to the screening questions to determine eligibility. The survey logic within REDCap will determine eligibility for participation based on participant responses. BuildClinical also had logic to determine eligibility. If they are ineligible, they will be notified after the survey is submitted. If they are eligible to proceed, they will be contacted by the study team via email to book a time to attend a live informational webinar.

We will not require PCP approval since we assess exclusionary medical conditions during the screening process. If conditions are reported that might put the participant at risk during the intervention, they will be excluded.

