Nutritional Literacy. We will report on the % who are considered likelihood of poor nutrition literacy, possibility of poor nutrition literacy, and likelihood of good nutrition literacy. History of Weight loss attempts, diet tracking and diet tracking apps. Using descriptive statistics, we will summarize those who have a history of weight loss attempts, and use of diet tracking and diet tracking apps.

Amount of tracking. We will report the amount of tracking participants did throughout the intervention as well as one month following the intervention.

Contamination. We will report the percentage of participants that used any outside programs that provided weight loss coaching or another app to help with weight loss/exercise.

Burden. Using descriptive statistics, we will summarize burden scores in both treatment conditions. ANOVAs will be used to compare conditions on burden.

Weight loss. We will calculate weight change from baseline to 8 weeks as well as baseline to 12-weeks. As this pilot trial is not powered to detect differences, average changes will not be compared by treatment condition.

Inclusion/Exclusion Criteria

List ALL inclusion and exclusion criteria. Any proposed exclusion criterion based on gender (women of childbearing potential), age, or race must include rationale for the exclusion.

Inclusion Criteria

- 18-65 years old
- BMI 27-45 kg/m²
- Wi-Fi connectivity at home
- Logs into Facebook at least 5 days per week over the past 2 weeks
- Able to participate in the study in English
- Interested in losing weight
- Lives in US

Age justification: Children under 18 require different programming for weight loss and maintenance given their developmental needs. Weight loss is for elderly adults should be medically supervised, something this study is not offering.

Exclusion Criteria

- Pregnant/lactating or plans to become pregnant during study period
- Reports having bipolar disorder, substance abuse, psychosis, an eating disorder, or severe depression
- Had bariatric surgery or plans to have surgery during the study
- Currently taking medication affecting weight
- Has lost ≥5% of weight in past 3 months
- Is participating or intends to participate in another weight loss program during the study
- Chronic pain that interferes with the ability to exercise
- Type 1 Diabetes
- Type 2 Diabetes
- Unable to make dietary changes or increase physical activity
- Unable to walk ¼ mile unaided without stopping

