- Currently smokes or vapes nicotine twice a week or more
- Has a digestive disorder/condition that precludes dietary changes
- Meets criteria for severe depression on the PHQ-8 (score of >19)
- Does not currently own a smartphone
- Participated in previous weight loss studies under the PI
- Unable to attend the orientation webinar
- Had major surgery in past 6 months and have not been cleared by their doctor to resume physical activity and diet changes
- Plans to have major surgery in the next 6-months
- Has an implanted cardiac defibrillator or pacemaker
- Did not complete screening and on-board processes of study (screening survey, webinar, e-consent, baseline survey, app set-up, scale set-up, etc.)
- Is a student and/or staff of the PI.

Removal from Study

Describe the conditions under which participants may be removed from the study, e.g., noncompliance with study rules, study termination, etc. \Box N/A

Participants will be removed from the study if: 1) they do not complete all screening, baseline, and on-boarding procedures (two surveys, consent, webinar orientation, app set-up, and scale set-up, join the Facebook group), 2) become pregnant during the study period, 3) post threatening or disturbing content in the Facebook group (e.g., bullying/harassment of others, hate speech, violent/graphic content, violating privacy of others etc.), and 4) if they choose to withdraw their participation from the study. Participants reporting that they would like to

withdraw from the study will be given the option to 1) withdraw from all intervention-related activity and contacts, but still complete the final assessment or 2) withdraw from the study completely with no additional study contact. If a participant becomes pregnant during the study, they will be withdrawn from the intervention, but will be asked to complete the follow-up assessments.

Potential Harms/Risks and Inconveniences:

Describe the potential risks to participants (and secondary participants, if applicable) and *steps taken to minimize risks* for each participant population. For each risk, you must assess the likelihood of occurrence, and, if it were to occur, the associated severity. Types of risks to consider include, but are not limited to: physical, psychological, social, legal, employment, and financial.

N/A (no foreseeable risks anticipated) or,
Describe any anticipated inconveniences the participants may experience (such as
their time, abstention from food, etc.): \square N/A

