Potential risks for being in this study includes injury while exercising and/or cardiovascular event, accidental exposure of personal information, and discomfort with study procedures (e.g., feeling uncomfortable with some questions asked on a survey or something someone said in Facebook group). The attempt to avoid risks to participants will be addressed by focusing mainly on suggesting moderate intensity exercise to avoid discomfort, pain, or injury. We do provide guidance on vigorous activity for those participants who prefer that type of exercise and/or are already doing it prior to joining the study in accordance with the National Exercise Guidelines. We also provide images or links on how to do exercises properly to avoid pain or injury. Participants reporting discomfort will be told to go see their PCP. Injuries are unlikely to occur since we screen out medical conditions that could make someone prone to injury. To avoid accidental exposure of personal information, tracking data will be stored electronically in REDCap, a network secure data entry program, in the UConn-supported R drive, or OneDrive which is secure. Only those who have IRB approval to work on the study will have access to the R drive and REDCap database for this study. To avoid discomfort during study procedures, participants will be informed that they may withdraw from the study at any time if they feel discomfort with any of the study procedures or if they don't want to answer a question on a survey, they can skip it. The likelihood of each of these risks happening is rare since we take steps to prevent these from happening and if they were to happen, the severity would be likely be minor.

Benefits:

Describe anticipated benefits to the individual participants. If test results will be provided, describe, and explain procedures to help participants understand the results. Identify who provides results to participants. If individual participants

may not benefit directly, state so here. Do not include compensation or earned course credits in this section.

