Participant retention

Engagement will be tracked during the intervention, and completion of follow-ups will be documented. Participants will be reminded of upcoming study assessments. If a participant chooses to drop from the intervention, they will be given the option to skip the rest of the intervention, but still complete the follow-up. Retention is reviewed and discussed weekly throughout the study and at follow-up. A final retention and engagement report will be provided in the safety report.

Data review (completeness/outliers):

Reports will include completeness of data (visits completed, % of expected forms submitted, % of submitted forms passing edit); missed visits and missing information within visits; descriptive

information for each endpoint (change in weight and physical activity) without statistical testing; and quality control analyses for primary outcome (change in weight). Data will be cleaned at the end of each phase (screening, intervention, and follow-up). A final data review report will be provided in the safety report.

4. Data evaluated for problems

Data reports will be reviewed by the data manager, statistician, and PI.

5. Actions taken during certain occurrences

Baseline participants who report conditions that could create a safety concern while receiving the intervention will be excluded. Adverse events that occur during the intervention will be assessed, recorded, and followed up until resolved. Safety monitoring procedures will be documented in a standard protocol and overseen by the PI and program director. Any adverse events will be immediately reviewed by the program director. The safety officers will be informed of all adverse events during data review. Serious adverse events will be communicated immediately to the PI and safety officers. The NIH and UConn IRB will be notified immediately in the event of serious adverse event. Any death of a study participant will be reported to the NIH and UConn IRB whether or not it appears to be related to the study.

6. IRB Communications

The program director and research coordinator will communicate with the IRB. Communication will occur through emails, phone calls, and/or InfoEd as necessary.

7. Informing sponsor procedures

The sponsor will be notified within 48 hours of serious events that the IRB recommends we report.

Are there any plans to do an interim analysis? ⊠ No □ Yes
If yes, describe the interim analysis plan:

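### PCP approval is waived because screening covers exclusionary conditions, yet the exclusion list names no cardiovascular disease, so no written criterion ensures that every applicant is asked about it

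*Protocol*

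**What the plan says.** Under Design, Procedures, Materials and Methods, the Screening paragraph waives physician sign-off and gives the reason: "We will not require PCP approval since we assess exclusionary medical conditions during the screening process". The next sentence is a general rule: "If conditions are reported that might put the participant at risk during the intervention, they will be excluded". Item 5 of Data Safety Monitoring has a similar one: "Baseline participants who report conditions that could create a safety concern while receiving the intervention will be excluded". The same Screening paragraph says how eligibility is decided: "The survey logic within REDCap will determine eligibility for participation based on participant responses". BuildClinical has its own logic for the people it recruits.

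Potential Harms/Risks and Inconveniences opens with: "Potential risks for being in this study includes injury while exercising and/or cardiovascular event".

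Inclusion/Exclusion Criteria answers a form prompt that reads "List ALL inclusion and exclusion criteria". The only cardiac entry in the exclusion list is "Has an implanted cardiac defibrillator or pacemaker".

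**The concern.** The waiver is only as strong as the set of conditions that screening covers. The protocol names a cardiovascular event as a risk of taking part, so a reader expects the list of conditions to include the diseases that most directly bear on that risk. It includes an implanted device and no disease.

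The general rules act on conditions that are reported, and a condition is reliably reported only if someone asks. Take a person with known coronary disease and no implanted device, who can walk a quarter mile and increase activity. If no other item applies, that person meets no listed exclusion. Exclusion then depends on an unseen question, or on the person mentioning the condition and staff applying the general rule. The programme's exercise goals follow, with no physician check beforehand.

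This is a matter of participant safety and of applying eligibility evenly. It does not bear on a sample size, an error rate or an endpoint.

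**Working it through.** The plan gives no figure to reproduce. The check is a count of the criteria and a comparison of sections.

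**1. Exclusion list (Inclusion/Exclusion Criteria).** There are 22 items.

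- Health conditions, treatments, nicotine use or physical limits, 15 items: pregnancy or lactation; psychiatric, substance or eating disorder; bariatric surgery; weight-affecting medication; chronic pain; type 1 diabetes; type 2 diabetes; inability to change diet or activity; inability to walk a quarter mile; nicotine; digestive disorder; PHQ-8 above 19; recent major surgery without clearance; planned major surgery; implanted cardiac device.
- Other items, 7: recent weight loss, another weight loss programme, no smartphone, earlier studies under the same investigator, webinar attendance, incomplete on-boarding, student or staff tie.
- Check: 15 + 7 = 22.
- Items naming a heart or vascular disease: 0. Items naming a cardiac device: 1.

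The list is specific elsewhere (both diabetes types have their own line), so the absence is not explained by a generic style. None of the 7 inclusion items is cardiac.

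**2. General rules.** There are two, in Screening and in Data Safety Monitoring item 5. Conditions named: 0. Both turn on what is reported, and neither is in the list.

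**3. Where could the condition be reported?**

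- *Screening survey.* The measures table gives it as the measure of the inclusion and exclusion criteria. It is not shown.
- *Telephone screening.* Recruitment procedures mention it only for Qualtrics-panel recruits, and its content is not given.
- *Baseline survey.* The Baseline paragraph lists demographics, nutrition literacy, depression, and history of weight loss attempts and diet tracking. No medical history is described.
- *Final eligibility check.* Staff review the steps already completed. No new medical question is described.

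So the described steps after screening add no cardiac question, and whether one is asked at screening cannot be seen.

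**4. How the risk text uses screening.** The harms section says: "Injuries are unlikely to occur since we screen out medical conditions that could make someone prone to injury". The Risk/Benefit Analysis likewise ties screening to injury or pain. The cardiovascular event is covered only collectively, by the general statements that each risk is rare and that the benefits outweigh all of them.

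**5. Capacity to absorb more screen failures.** The plan expects about 1,500 screened for 108 enrolled: 1,500 / 108 = 13.9 per enrolled participant. The protocol says many of the 1,500 will be incomplete responses, so this ratio overstates the pool of usable applicants and gives only rough reassurance.

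**The case against.** The strongest reply is that the plan already handles the case. Known coronary disease, once reported, falls plainly under both general rules, and the list and the rules can work together without contradiction. This stands. A reader might infer that the protocol admits people with known heart disease, or that it never asks about it. The documents support neither. The rules would exclude such a person on report, and the survey may well contain the question. Its absence from the public document shows nothing about its content.

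Other safeguards also stand. Age is capped at 65, with the stated reason that weight loss in elderly adults calls for medical supervision. The walking and activity criteria, the diabetes and nicotine exclusions and the item on uncleared recent surgery remove some people at higher cardiac risk. Staff carry out a final eligibility check before randomisation, where a general rule can be applied. Participants who report discomfort are told to see their PCP.

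A reader who sees only the weekly targets (150-300 minutes of moderate/vigorous exercise, or 75-150 of vigorous) might also infer a heavy exertional load. The Intervention section gives brisk walking and gardening among its examples and builds up by weekly steps. The harms section says that mainly moderate exercise is suggested, with guidance on vigorous activity for those who prefer it or already do it.

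What the reply does not answer is the dependence on reporting. An unnamed condition cannot be coded into survey logic from the written criteria, and nothing in those criteria makes sure that applicants from all recruitment routes get the same question. Nor is this a detail to leave to an analysis plan: eligibility criteria belong in the protocol, and the form asks for all of them.

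**Conclusion.** The point holds for the written criteria. PCP approval is waived on the strength of condition screening and a cardiovascular event is a named risk, but 0 of 22 exclusions name a cardiovascular disease, 1 names a cardiac device, and the 2 general rules name no condition. No written criterion ensures that everyone is asked.

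This rests on reading the list as the full set of specific criteria, as the form's prompt implies, and on the protocol's description of the baseline survey and final check being complete. It does not rest on any assumption about the screening survey. If the survey already asks, the remaining defect is that the criterion is not written down.

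The residual risk is limited by the safeguards above. The number of people with heart disease who might enrol, and their event risk, cannot be estimated from the documents. The change is a cheap safety improvement and worth making. It is not evidence that the trial is unsafe, and no effect on the randomised comparison is claimed.

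**What to change.** Add one item to the exclusion list and to the REDCap, Qualtrics and BuildClinical versions of the screening survey:

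*Known cardiovascular disease (e.g., prior heart attack or stroke, coronary disease, heart failure, exertional chest pain), unless cleared by their doctor for physical activity and diet changes.*

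The clearance route follows the one the list already uses for recent major surgery. If the survey already asks, copy its item into the list and check that all versions carry it. Also place the general rule from the Screening paragraph in the list.

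The cost is a short protocol and survey amendment and a few more screen failures. The item would still rely on self-report: the gain is a direct question put the same way to every applicant, not verification.

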The **Daily Tracking Group** will be given the traditional prescription of tracking every day during the 8-week intervention. The **1 On/1 Off Tracking Group** will be asked to track every day for a week, then to take a week off, and so on throughout the 8 weeks. This group will then track on weeks 1, 3, 5, and 7 for a total of 4 weeks of tracking. Although this group will only be tracking at the most 50% of the time, our previous study found that tracking 40% of the time was the threshold needed to lose ≥5% of weight which is the lower end of the program weight loss goal (5-10%). The **2 On/1 Off Tracking Group** will be asked to track every day for 2 weeks, then to take 1 week off, and so on throughout the 8 weeks. This group will then track on weeks 1, 2, 4, 5, 7, and 8, for a total of 6 weeks of tracking. Although this group will only be tracking at the most 67% of the time, our previous study found that tracking 67% of the time was the

threshold needed to lose ≥10% of weight which is the high end of the program weight loss goal (5-10%).

All three groups will be asked to continue their schedule of tracking in the month following the 8-week intervention (i.e., 12 weeks). We will compare groups on weight loss at 8 weeks, total days of tracking over 8 weeks, % who adhered to their prescription during the 8 week program, % who tracked <50% of the time, % who tracked >67% of the time, tracking burden, tracking enjoyment, intentions to continue tracking past 8 weeks, number of days tracked in the subsequent month, and weight loss at 12 weeks. Findings will inform a fully powered clinical trial of tracking prescriptions during a full-length weight loss program (6 months in duration).

Provide a clear and succinct summary description of the background information that led to the plan for this project:

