One approach to improving food tracking adherence is to reduce the burden of the task by simplifying the prescription. Simplification may involve reducing the frequency (e.g., 5 days a

week versus every day) or reducing the amount of intake to track (e.g., some foods/meals vs all foods/meals). To reduce burden, some studies had participants track diet patterns or servings of food groups (instead of calories) and others had participants track by taking photos of their food¹³. A recent systematic review found that 3 out of 4 studies using such abbreviated food tracking approaches reported an association between food tracking and weight loss¹³, which is evidence that the prescription of tracking everything all the time may not be necessary¹⁵. The only approach to tracking that was not associated with weight loss was where participants took photos of foods¹⁶, which suggests this approach may be too far afield from the traditional tracking method to produce meaningful impacts on weight.

We recently conducted an analysis of 153 participants of a digitally delivered weight loss program and found that the optimum threshold of diet tracking that predicted ≥3%, ≥5%, and ≥10% weight loss at 6 months was tracking on 28.5%, 39.4%, and 67.1% of intervention days, respectively. That participants could track about two-thirds of the time and still lose 10% of their baseline weight is an encouraging sign that perfect food tracking adherence is not necessary to be successful. Because participants can reach the weight loss goal while tracking 40-67% of the time, perhaps tracking prescriptions that match those levels would result in less burden and the same or higher success rate. The purpose of this study is to test this very question.

Provide references as appropriate and, when applicable, previous work in animal and/or human studies:

References are provided at the end of the protocol.

Provide previous UConn protocol number, if applicable:

N/A

For each participant population proposed for this study, what is the total # of participants (or, for record reviews, total # of records) required to answer the study question:

The total number of subjects that will be enrolled into the study is 108. It is estimated that we will screen ~1,500 participants to achieve this recruitment goal. Since the initial contact is via an online link, there will be many incomplete responses driving up the number of screened-out participants.

Justification of Sample Size:

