For qualitative and pilot studies, describe how the proposed sample size is appropriate for achieving the anticipated results. For quantitative studies, provide a power analysis that includes effect size, power, and level of significance with references for how the sample size was determined. Explain the rate of attrition and possible number who fail the screening, with references as appropriate.

Leon et al state "power analyses should not be presented in an application for a pilot study that does not propose inferential results."17 As they and others recommend,17,18 we based the sample size of 108 on necessities for examining feasibility thus identifying modifications required to the trial design or study procedures before conducting the full-scale factorial trial. Having 108 participants allows us to recruit online groups of 36, which our previous work shows is feasible and breeds regular engagement.

Enrollment of Oconn Students and/or Employees:
Will UConn students be enrolled?
\square No \boxtimes Yes -> Is it possible that any of the listed study key research personnel teach, or are supervisors of, any of the students?
\boxtimes No \square Yes -> Provide justification for inclusion of this population, provide name of the member of key personnel, and explain how undue influence and bias will be prevented:
Will UConn employees be enrolled?
\square No \boxtimes Yes -> Is it possible that any of the employees report to one or more study key personnel?
$oxtimes$ No \oornightarrow Yes -> Provide justification for inclusion of this population, and explain how undue influence and bias will be prevented:
UConn students and employees may be enrolled if they meet eligibility requirements and are interested in completing the study. Students or employees that report to, are taught by, or have supervisors on key personnel of this project will be excluded from participation.
Enrollment of Key Personnel, Spouses or Dependents/Relatives: Will study key personnel, spouses of study key personnel, or dependents/relative.

S of any study key personnel be enrolled in the study?

 \boxtimes No \square Yes -> Specify, provide justification for inclusion of this population, and explain how undue influence and bias will be prevented:

Recruitment procedures:

For each participant population, provide full detail:

How will the participants be notified or approached about the research (include copies of all recruitment tools, in any media)?

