As a result of the COVID-19 Pandemic, our lab is working remotely. Therefore, any phone calls or texts made to participants while our team members are working from home will be conducted via Google Voice. This is an app that gives our staff a different phone number to protect their personal information due to their inability to divert UConn phone lines to personal phones. We will not be recording any phone calls with Google Voice. Participants will be able to reach out to investigators as easily as standard calling. Participants do not need the app to contact the lab. Researchers will retain the call history and text message exchanges for the duration of the study within the Google Voice app. Call history and text messages will be deleted once the study is over. If something sensitive is shared by a participant, we will delete it right away and save it in the R Drive or REDCap if it is relevant to the study. Team members using Google Voice to communicate with participants will ensure their phones are properly maintained during the study for security and privacy purposes. It is important to note that some information may be retained on Google's active servers temporarily for billing UConn staff or other business purposes, and residual copies may remain in Google's backup systems. Anonymized copies of call record information, with no personally identifiable information, will be retained on Google systems to meet reporting and auditing requirements. However, this is no different than any standard phone plan.

Baseline. Participants that decide to complete the online consent process will be sent the online baseline survey about demographics, nutrition literacy²⁸, depression, and history of

weight loss attempts and use of diet tracking and diet tracking apps. Participants who do not consent will be brought to a landing page thanking them for their time learning about the study, but they will no longer be eligible to participate beyond that point.

After the baseline survey is completed, for those that are still eligible, UConn will ship a study scale to the participants. Once the participants receive their scale, UConn staff will give the participant an option to set it up themselves or schedule a call to help them set up the scale and ensure that it is working, and we can access their data. UConn staff will then collect a baseline weight from participants to confirm their BMI for eligibility reasons.

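### Burden is compared by ANOVA with no covariate, although gender stratifies the randomisation and prior tracking is known at baseline: valid, but possibly less precise than it could be

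*Protocol*

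**What the plan says.** **Before randomisation.** Under Design, Procedures, Materials and Methods (Baseline), the survey covers, among other things, "weight loss attempts and use of diet tracking and diet tracking apps". The same section makes completion of the baseline survey a condition of being randomised. Under Study Design the Protocol states "Participants will then be randomized (stratified by gender", and names no other factor.

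**Analysis.** The only use given for the tracking-history item, under Data Analysis, is: "Using descriptive statistics, we will summarize those who have a history of weight loss attempts, and use of diet tracking and diet tracking apps". For burden the section says "ANOVAs will be used to compare conditions on burden", with no covariate.

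**Days tracked.** The Purpose/Introduction promises: "We will compare groups on weight loss at 8 weeks, total days of tracking over 8 weeks". Data Analysis says only that the amount of tracking will be reported, with no test or model.

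**Size and status.** "The total number of subjects that will be enrolled into the study is 108", and "Having 108 participants allows us to recruit online groups of 36". No power analysis is given. The sample-size section cites guidance that "power analyses should not be presented in an application for a pilot study that does not propose inferential results".

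**The concern.** The pilot asks whether scheduled breaks ease the load of tracking. Burden is collected only at follow-up #1, so it has no baseline value to adjust for. Among the listed baseline measures, earlier use of tracking and tracking apps is the closest available proxy for how a participant will find the task. No eligibility criterion removes experienced trackers, so the sample may mix people used to logging with people new to it. With about 36 per arm and no stratification on this item, the arms can differ on it by chance.

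Gender has a separate claim to be in the model. If it predicts burden, stratification has already balanced it across arms, but the plain ANOVA leaves its variance in the error term. The standard error is then somewhat larger than the design warrants.

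At stake are the precision of the burden contrasts and how far the observed estimates reflect the schedules rather than who was allocated where. The Protocol says the findings will inform a fully powered trial, so these estimates will be carried forward.

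**Working it through.** **1. The plan's own figure.** 3 arms × 36 = 108, which reproduces the enrolment total. Equal allocation is assumed, because no ratio is stated. Burden is a follow-up measure, so attrition would make the analysed arms smaller than 36.

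**2. Chance imbalance in prior tracking.** The prevalence p is not in the Protocol; 30% to 70% is assumed. The standard error of a between-arm difference is √(2p(1−p)/36).
- p = 0.5: √(0.50/36) = 0.118
- p = 0.3 or 0.7: √(0.42/36) = 0.108

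In 400,000 simulated three-arm draws, a given pair of arms differed by 20 points or more in 5% to 8% of trials. Some pair did so in 13% to 18%.

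**3. What a 20-point gap does to the estimate.** Let ρ be the correlation between prior tracking (treated as binary) and the outcome. Prior trackers then differ from others by ρ/√(p(1−p)) SD, which is 2ρ at p = 0.5. The shift in an arm contrast is 0.20 × 2ρ = 0.4ρ SD.

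**4. Precision.** Adjustment multiplies the variance by 1 − ρ², so the standard error falls by the factor √(1 − ρ²). The equivalent sample size is 108/(1 − ρ²). The pairwise detectable difference at an assumed 5% level and 80% power is (1.960 + 0.842) × √(2/36) = 0.66 SD unadjusted.

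| Assumed ρ | Shift from 20-point gap (SD) | SE factor | Equivalent N | Detectable difference (SD) |
|---|---|---|---|---|
| 0.1 | 0.04 | 0.995 | 109 | 0.66 |
| 0.3 | 0.12 | 0.954 | 119 | 0.63 |
| 0.5 | 0.20 | 0.866 | 144 | 0.57 |

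**5. Charge for degrees of freedom.** Two one-degree-of-freedom covariates take the residual degrees of freedom from 105 to 103. An approximate factor that gives gender no credit for explaining burden is √((1 − ρ²) × 105/103).
- ρ = 0.1: √(0.99 × 1.0194) = 1.005
- ρ = 0.3: √(0.91 × 1.0194) = 0.963
- ρ = 0.5: √(0.75 × 1.0194) = 0.874

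On this reckoning the break-even is ρ = √(2/105) = 0.14. A separate missing category costs a third degree of freedom and moves it to √(3/105) = 0.17.

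**6. Validity of the stated ANOVA.** This was simulated with 8,000 trials per setting, p = 0.5 and prior tracking as the only covariate. Type I error was 4.6% to 5.2% unadjusted and 4.7% to 5.4% adjusted, at a nominal 5%. With arm means 0, 0.25 and 0.5 SD, power moved from about 0.46 to 0.46 (ρ = 0.1), 0.45 to 0.49 (ρ = 0.3) and 0.45 to 0.56 (ρ = 0.5).

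**The case against.** The strongest reply is that nothing here is an error. A one-way ANOVA on randomised arms is valid, and the simulation in step 6 agrees. Covariates are often left to a statistical analysis plan, which is not at hand, and a descriptive use of the item does not rule out another. That largely stands and sets the severity. It does not remove the point, because the Protocol does name both the test for burden and the use of the item, and a better choice is open to it.

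Three stronger readings are tempting and are not supported.
- **That the burden comparison is biased.** It is not. Chance imbalance is already covered by the test's error rate. Adjustment improves the estimate given the imbalance drawn and may tighten it.
- **That days tracked is also fixed as an unadjusted comparison.** The Purpose/Introduction promises a comparison without a method, and Data Analysis only reports amounts. There is no specified unadjusted analysis to fault, and the mismatch between the two sections is a separate matter.
- **That prior tracking is an established predictor.** The Protocol says nothing on this. The measures table also lists burden under Intervention Feedback, apart from the tracking-acceptability scales, so the outcome may be broader than tracking burden and the correlation weaker. If nearly all participants have used an app, a yes/no version would carry little information.

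Other objections bear on the remedy and are accepted. Gender, as the stratification factor, belongs in the model. The format of the investigator-derived history item is not shown, so a yes/no coding cannot be presumed. The Privacy/Confidentiality section lets participants skip baseline questions, so some values may be missing.

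**Conclusion.** The point holds as a low-severity improvement to the one named between-arm test. The ANOVA on burden is valid. By naming neither the stratification factor nor a relevant baseline item, it may give up precision and leaves the estimate exposed to the imbalance actually drawn.

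For assumed correlations of 0.1 to 0.5 the standard error would fall by about 0.5% to 13%. After a cautious charge for degrees of freedom, the range runs from a negligible loss to about 12.6%. A 20-point imbalance in prior tracking, seen between some pair of arms in 13% to 18% of trials, would move a contrast by 0.04 to 0.20 SD at 50% prevalence.

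All of this rests on assumed prevalence and correlation, 36 analysed per arm and a binary item. In a pilot with no power analysis, no design conclusion turns on it.

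**What to change.** In Data Analysis, under Burden, replace the ANOVA with a linear model containing three-level arm, gender, and prior use of tracking or tracking apps in the form recorded at baseline. State beforehand how skipped history items are handled, by a missing category or a simple imputation. Report the unadjusted result alongside, and show prior use by arm in the baseline table. If arms are compared on days tracked, as the Purpose/Introduction promises, use the same covariates there.

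Naming the covariates now also prevents a choice made after imbalance has been seen. The cost is a few lines of text and two or three degrees of freedom, with no new data, contacts or participants. The downside is a gain that may be nil if prior use predicts burden only weakly.
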